8.2 RETREATMENT

To avoid any permanent risk of under- or overcorrection for the patient, a retreatment will be performed if necessary as done in daily routine practice. However, retreatments will not be performed earlier than the 12-month time point in order to collect the study data.

9.0 STATISTICS

9.1 STATISTICAL METHODS

The main criterion and secondary criteria represent the standard analysis of refractive and visual outcomes and will be analyzed according to the Standard Graphs for Reporting Refractive Surgery, as recommended by the Journal of Refractive Surgery.⁵⁴

| | | |
|------------|-------------|----------------------------|
| 01/02/2016 | Version 3.0 | CONFIDENTIAL Page 18/28 |
|------------|-------------|----------------------------|

9.2 DETERMINATION OF SAMPLE SIZE

The main criterion for the study is to evaluate the standard deviation of the $SE_{\text{postop}} - SE_{\text{target}}$, which represents the scatter of the refractive outcome. This metric was chosen in place of the predictability of the refractive correction as a mean under or overcorrection can be adjusted for simply using a nomogram, so the scatter is an indicator of the best possible refractive predictability.

To calculate the sample size for this study, the standard deviation of the refractive outcome will be compared to that reported for LASIK for an equivalent range of myopia. In a previous study of 480 eyes using the MEL80 excimer laser for myopia between -8.00 and -14.00 D, we found the standard deviation of the spherical equivalent refraction 1 year after LASIK to be 0.70 D.⁵⁶ A one-tailed F-test will be used to test if the variances of the two populations are equal, or that the variance of SMILE is not greater than the variance of LASIK, using a difference of 0.15 D in standard deviation.

Null hypothesis: $\text{Variance(LASIK)} = \text{Variance(SMILE)}$

Test hypothesis: $\text{Variance(LASIK)} < \text{Variance(SMILE)}$

Given standard deviations of 0.70 and 0.85 D, the ratio of variances is 1.47. Using an α error probability of 0.05 and a statistical power (1- β error probability) of 0.8, the a priori sample size calculation indicates that a population size of 168 eyes is required.

The 1 year follow-up rate for routine refractive surgery patients at London Vision Clinic has been >90%, so it is reasonable to expect this level of follow-up would be achieved for the study population. Therefore, a total population of 187 eyes is required.

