| TITLE OF THE STUDY: VisuMax femtosecond laser small incision lenticule extraction (SMILE) for the correction of high myopia. | |
| DEVELOPMENT PHASE: Investigator Initiated Trial (IIT) | |
| METHODOLOGY: Prospective, single-center, non-randomized, including primary and secondary endpoints | |
| GENERAL OBJECTIVE: The objective of this clinical trial is to evaluate the safety and effectiveness of the Carl Zeiss Meditec VisuMax™ femtosecond laser small incision lenticule extraction (SMILE) procedure for the reduction or elimination of myopia for manifest refraction spherical equivalent (MRSE) up to -14.00 D with maximum 7.00 D cylinder (myopia with or without astigmatism). | |
| NUMBER OF PATIENTS: 187 eyes | |
| INVESTIGATIONAL DEVICE : VisuMax femtosecond laser | |
| DURATION OF TREATMENT: The overall treatment phase for all patients will be about 24 months | |
| DURATION OF FOLLOW-UP FOR EACH PATIENT: 1 year | |
| START OF STUDY: February 2016 | |
| Interim Report: February 2017 | |
| FINAL REPORT: September 2019 | |
| MAIN INCLUSION CRITERIA: - Patients with high myopia with or without astigmatism for MRSE between -9.00 D and -14.00 D, who would like to undergo SMILE surgery with the VisuMax femtosecond laser system | |
| MAIN EXCLUSION CRITERIA: - Patients, who are not medically suitable for laser refractive surgery | |

LIST OF ABBREVIATIONS AND DEFINITIONS

| | |
|----------------------|---|
| Astigmatism | Refractive error, caused by an irregularly shaped cornea with one meridian being significantly more curved than the meridian perpendicular to it |
| Cap | Corneal tissue above the refractive lenticule that remains intact except for a small incision through which the refractive lenticule is removed |
| CDVA | Corrected Distance Visual Acuity |
| CE | Conformité Européenne |
| CZM | Carl Zeiss Meditec |
| D | Diopter |
| eCRF | electronic Case Report Form |
| EMR | Electronic Medical Record |
| GCP | Good Clinical Practice |
| HOA | Higher Order Aberrations |
| LASIK | Laser in situ Keratomileusis |
| MPG | Medizinproduktgesetz - Medical Devices Act |
| Myopia | Nearsighted or shortsighted |
| MRSE | Mean Refractive Spherical Equivalent (=sphere + cylinder/2) |
| PRK | Photorefractive Keratectomy |
| RST | Residual Stromal Thickness |
| SAE | Serious Adverse Event |
| SLT | Sub-lenticule Thickness |
| SMILE | Small Incision Lenticule Extraction |

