excimer laser ablation are avoided, such as stromal hydration,⁴⁶ laser fluence projection and reflection losses,^{47, 48} and other environmental factors.⁴⁹ In SMILE, the tissue removal is defined only by the accuracy of the femtosecond laser, which is not affected by any changes in environmental conditions. Therefore, the accuracy of the lenticule interfaces will be independent of the overall thickness of the lenticule (i.e. the amount of correction), meaning that the potential error due to the surgery will be the same for low and high myopia.

These factors should also reduce the induction of higher order aberrations, particularly spherical aberration, compared to LASIK as has been shown for moderate myopia.^{50, 51} The induction of spherical aberration should be reduced both by the increased contribution of the anterior stroma thereby reducing the peripheral stromal expansion postoperatively,^{52, 53} as well as the elimination of the laser fluence projection and reflection losses that degrade the peripheral ablation.^{47, 48}

Therefore, the introduction of SMILE has the potential to improve the outcomes of corneal refractive surgery for very high myopia in terms of accuracy, safety, and quality of vision (induction of aberrations). This study will investigate safety and effectiveness for high myopia with sphere -10.00 D or higher treated by SMILE with the VisuMax femtosecond laser system.

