3.0 STUDY OBJECTIVES

The primary objective of this study is to evaluate the safety and efficacy of the Carl Zeiss Meditec VisuMax™ femtosecond laser SMILE procedure for the reduction or elimination of myopia with spherical equivalent from -9.00 D to -14.00 D with a maximum cylinder of 7.00 D (high myopia with or without astigmatism). The secondary objective of the study is to establish appropriate safety parameters for SMILE surgery given that they have been set to be the same as LASIK.

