4.0 STUDY ENDPOINTS

4.1 MAIN ENDPOINT

1. Standard deviation of $SE_{postop} - SE_{target}$ at each follow-up time point (represent the scatter of the refractive outcome)
2. Difference in keratometry between the 3 months and 12 months' time points to be the same as for group of matched LASIK eyes.

| | | |
|------------|-------------|----------------------------|
| 01/02/2016 | Version 3.0 | CONFIDENTIAL Page 10/28 |
|------------|-------------|----------------------------|

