6.1.2 Inclusion criteria specific to the protocol

- Eyes with high myopia spherical equivalent between -9.00 D up to -14.00 D, with cylinder up to 7.00 D will be included.

| | | |
|------------|-------------|----------------------------|
| 01/02/2016 | Version 3.0 | CONFIDENTIAL Page 12/28 |
|------------|-------------|----------------------------|

- Calculated sub-lenticule thickness (SLT) $\geq 220 \mu\text{m}$
- Calculated total uncut stromal thickness (TUST) $\geq 300 \mu\text{m}$
- The corrected distance visual acuity will be 20/40 or better in each eye pre-operatively.
- Patient will be able to understand the patient information and willing to sign an informed consent.
- Patient will be willing to comply with all follow-up visits and the respective examinations as specified in the flow-chart.

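### The LASIK benchmark for the variance test covers -8.00 to -14.00 D on an unstated scale, SMILE enrols SE -9.00 to -14.00 D, and nothing aligns the two

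*Combined protocol and SAP*

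**What the plan says.** Section 9.2 (Determination of Sample Size) makes the main criterion the standard deviation of postoperative SE minus target SE. This SD "will be compared to that reported for LASIK for an equivalent range of myopia". The benchmark follows: "In a previous study of 480 eyes using the MEL80 excimer laser for myopia between -8.00 and -14.00 D, we found the standard deviation" of SE one year after LASIK to be 0.70 D. A one-tailed F-test is specified, with equal variances as the null and a larger SMILE variance as the alternative. It uses SDs of 0.70 and 0.85 D, alpha 0.05 and power 0.80, and arrives at 168 eyes, or 187 after allowing for follow-up.

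The SMILE population is defined on SE. Section 6.1.2 says "Eyes with high myopia spherical equivalent between -9.00 D up to -14.00 D, with cylinder up to 7.00 D will be included", section 3.0 says "myopia with spherical equivalent from -9.00 D to -14.00 D with a maximum cylinder of 7.00 D", and the synopsis says "Patients with high myopia with or without astigmatism for MRSE between -9.00 D and -14.00 D".

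Matching is mentioned once, in section 4.1, for the second main endpoint: the 3-to-12-month keratometry change is "to be the same as for group of matched LASIK eyes". Section 9.1 names only the standard refractive graphs.

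**The concern.** The trial is non-randomized with an external comparator, so the comparability of the two SDs rests on how the LASIK eyes are chosen. As printed, the LASIK range starts 1.00 D lower than the SMILE range. Its scale is not given in section 9.2 or in the title of the cited LASIK study, and no LASIK cylinder limit is stated. No rule in the plan brings the two groups onto the same range for the F-test.

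The null hypothesis of equal scatter is informative only at comparable myopia. If LASIK scatter depends on preoperative SE, the 0.70 D answers for a somewhat different population. A rejection, or a failure to reject, could then partly reflect case mix rather than procedure. A reader of the main result could not tell whether this had happened.

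**Working it through.** **1. The plan's own figure.** Inputs from section 9.2: SDs 0.70 and 0.85 D, one-sided alpha 0.05, power 0.80. With R the true variance ratio SMILE/LASIK, power = P[F(n1-1, n2-1) > Fcrit / R].

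- R = (0.85/0.70)² = 1.4745 needs 166 eyes per group; the rounded 1.47 needs 169. The stated 168 lies between.
- At 168 v 168, power is 0.805 (R = 1.4745) or 0.799 (R = 1.47).
- 168/0.9 = 186.7, so 187.
- With LASIK fixed at 480 eyes, only 98 to 100 SMILE eyes would be needed, and 168 v 480 has power 0.921. The 168 therefore corresponds to equal groups. The number of LASIK eyes that will enter the test is not stated.

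**2. Sensitivity to the benchmark.** Suppose SMILE truly has the LASIK SD for SE -9 to -14 D, call it s, but is tested against 0.70 D. The false-rejection rate is the same formula with R = (s/0.70)². Example, 168 v 480: Fcrit = 1.2255. For s = 0.72, R = 1.058, Fcrit/R = 1.158, and the rate is 11.7% (10.0% at 168 v 168).

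**3. Both ranges on SE.** The documents give neither the LASIK SE mix nor any relation between scatter and myopia, so both are assumed here:

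- LASIK SD proportional to |SE|^g, with a pooled SD of 0.70 D on 8 to 14 D;
- density of |SE| proportional to exp(-λ(|SE|-8)), with λ = 0, 0.25, 0.5, which puts 17%, 29% and 41% of LASIK eyes at SE -8 to -9 D;
- SMILE eyes with the same mix as the LASIK eyes at -9 to -14 D;
- normal, independent eyes.

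Ranges below run over λ.

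| g | LASIK SD on SE -9 to -14 D | False rejection, 168 v 480 |
|---|---|---|
| 0 | 0.700 | 5% |
| 0.25 | 0.708 to 0.715 | 7% to 10% |
| 0.5 | 0.716 to 0.731 | 10% to 17% |
| 1 | 0.729 to 0.760 | 16% to 37% |

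At 168 v 168 the g = 0.25 row becomes 7% to 9%.

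**4. LASIK range on sphere.** The abbreviations list defines SE as sphere plus half the cylinder, so in magnitude each LASIK eye moves up by half its cylinder. Assume one fixed cylinder for all LASIK eyes, g = 0.25, 168 v 480.

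| Cylinder | Share below SE 9 D | Share above SE 14 D | False rejection |
|---|---|---|---|
| 1.00 D | 8% to 23% | 2% to 8% | 5.1% to 6.7% |
| 2.00 D | 0% | 3% to 17% | 3.5% to 4.5% |

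The direction therefore depends on the unstated scale as well as on the unknown growth.

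**The case against.** The strongest reply is that no error is demonstrated. If both ranges are SE, they share 5 of 6 D and the same upper limit. Equivalent need not mean identical, and the LASIK limits are printed next to the word. Every magnitude above comes from an assumed growth, SE mix or cylinder. The mild-growth shift to 0.708 to 0.715 D is small beside the benchmark's own 95% interval (0.66 to 0.75 D for an SD of 0.70 D from 480 independent normal eyes) and beside the 0.15 D difference of interest. In the SE-with-growth case the error counts against SMILE, so it would not produce a false claim in its favour. Truncating to common limits does not equalize the distributions either.

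Most of this stands, and it limits the weight of the point. The sampling-error argument stands only in part: the F-test allows for random error in the LASIK SD, not for a systematic shift. None of it supplies an alignment rule. The keratometry matching in section 4.1 is not one, because it is not attached to the SD endpoint.

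A reader might infer more than the documents support:

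- *That the sample size is wrong.* It reproduces.
- *That the test is biased against SMILE, or in its favour.* Section 2.0 argues that SMILE avoids excimer errors and that its surgical error is the same for low and high myopia. It does not say or quantify that LASIK scatter rises with myopia, and the scale of the LASIK range is unknown.
- *That other loose wording settles the scale.* The rationale's sphere-based description of the SMILE population says nothing about the LASIK range. The one-eye difference between section 9.2 (480) and the cited title (481) is negligible.

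**Conclusion.** The point holds as a matter of comparability. The benchmark for the only hypothesis test the plan specifies comes from a range that differs from the enrolment range as printed and has no stated scale, and nothing aligns the groups. Whether this biases the test is undetermined:

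- no bias if LASIK scatter does not change with myopia;
- too strict on SMILE if scatter grows and the LASIK range is SE;
- near nominal or slightly lenient under mild growth if the range is sphere.

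The illustrated error rates run from 3.5% to 37% against a nominal 5%. That spread reflects the assumptions and is not an estimate. The change is worth making because it is cheap and lets the main result be read, not because a stated figure is wrong.

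**What to change.** In section 9.2:

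1. State whether the LASIK range is sphere or SE.
2. Take the LASIK SD of SE minus target, at about 12 months, and its n from the investigators' LASIK eyes with preoperative SE -9.00 to -14.00 D.
3. Use that SD and n in the F-test and restate power for that n, keeping the 0.15 D difference.
4. Report the preoperative SE distribution of both groups, because common limits do not make them equal.
5. Keep the full -8.00 to -14.00 D cohort as a sensitivity analysis.

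**Cost.** This is a small re-analysis of data the plan presents as the investigators' own. It depends on LASIK targets, preoperative SE and visit dates having been recorded, which the documents do not say.

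The downside is fewer LASIK eyes. Under the assumed mixes, 281 to 400 of 480 remain. Power of 168 SMILE eyes for a 0.15 D difference is then about 0.83 to 0.91, against 0.92 with 480. If only 168 LASIK eyes were used, power would be 0.75 to 0.80 over recomputed SDs of 0.76 down to 0.70 D. Holding 0.80 with 168 SMILE eyes takes at least 164 LASIK eyes at an SD of 0.70 D and 223 at 0.76 D, which is why the LASIK n should be written down.

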5.0 STUDY DESIGN

This is a prospective single-center clinical trial in which a maximum of 187 eyes will be consented, enrolled, and treated with the VisuMax™ femtosecond laser.

Study subjects will be followed for 12 months. Subjects will be screened for eligibility, and informed consent will be obtained from those who meet screening criteria and are interested in participating in the study. Eligible subjects will be examined preoperatively to obtain a medical history and to establish a baseline ocular condition. Baseline and postoperative measurements will include manifest refraction, cycloplegic refraction, distance visual acuity (best corrected and uncorrected using ETDRS charts), slit-lamp examination, fundus examination, corneal topography and wavefront, corneal tomography (front and back corneal surface), central corneal pachymetry, dynamic pupillometry (dark, scotopic, and mesopic), whole-eye wavefront analysis, mesopic contrast sensitivity, and intraocular pressure (IOP).

All baseline and postoperative measurements will be done in accordance to the daily routine procedure of the clinic for standard SMILE treatments.

Retreatments of the study eye will not be allowed during the course of the study.

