6.2 EXCLUSION CRITERIA

6.2.1 General exclusion criteria

- Previous intraocular or corneal surgery of any kind on the eye being treated
- Patient not being able to lie flat in a horizontal position
- Patient not being able to tolerate local or topical anesthesia
- Autoimmune diseases
- Sicca syndrome, dry eye
- Herpes viral (herpes simplex) infections
- Herpes zoster
- Diabetes
- Pregnant or nursing women (or who are planning pregnancy during the study)
- Patients with a weight of $> 135 \text{ kg}$
- Any residual, recurrent or acute ocular disease or abnormality of the eye, e.g.
 - Cataract
 - Suspected glaucoma
 - Corneal disease
 - Corneal thinning disorder, e.g. keratoconus,
 - Pellucid marginal corneal degeneration
 - Dystrophy of the basal membrane
 - Corneal oedema
 - Exudative macular degeneration
 - Infection
- Any residual, recurrent, or active abnormality of the cornea to be treated, e.g.
 - Existing corneal implant
 - Corneal lesion

| | | |
|------------|-------------|--------------|
| 01/02/2016 | Version 3.0 | CONFIDENTIAL |
| | | Page 13/28 |

- Unstable refraction
- Connective tissue disease
- Dry eye

The complete list of contraindications is included in the Surgical Information Package provided to the patient by the London Vision Clinic before surgery. Furthermore, the contraindications related to a SMILE treatment correspond to those reported in the medical literature for laser refractive surgery.

| | | |
|------------|-------------|----------------------------|
| 01/02/2016 | Version 3.0 | CONFIDENTIAL Page 14/28 |
|------------|-------------|----------------------------|

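### The primary F-test treats eyes as independent although both eyes of a patient may enter, so its 5% error rate and 80% power are not assured

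*Combined protocol and SAP*

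**What the plan says.** - **Test (9.2).** "A one-tailed F-test will be used to test if the variances of the two populations are equal". The alternative is that SMILE has the larger variance. The inputs are standard deviations of 0.70 D (LASIK) and 0.85 D (SMILE), alpha 0.05 and power 0.80. They lead to 168 eyes, raised to 187 using a one-year follow-up rate observed in patients.
- **Comparator (9.2).** "In a previous study of 480 eyes using the MEL80 excimer laser", again counted in eyes, with no number of patients.
- **Unit of enrolment.** The Synopsis fills its patient field with eyes: "NUMBER OF PATIENTS: 187 eyes". Section 5.0 says "a maximum of 187 eyes will be consented, enrolled, and treated".
- **Eligibility (6.1.2).** "Eyes with high myopia spherical equivalent between -9.00 D up to -14.00 D", so the refractive criterion applies eye by eye.
- **Singular wording.** Section 5.0 says "Retreatments of the study eye will not be allowed during the course of the study", and 6.2.1 excludes "Previous intraocular or corneal surgery of any kind on the eye being treated". Both fit a criterion applied to each treated eye. Neither restricts a patient to one eye.
- **Analysis (9.1).** The endpoints "will be analyzed according to the Standard Graphs for Reporting Refractive Surgery". No section mentions fellow-eye correlation, clustering, a design effect or selection of one eye.

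**The concern.** A two-sample variance-ratio test takes its critical value from the F distribution with n - 1 degrees of freedom per group. That is valid only if all observations are independent. If some patients contribute both eyes and the two errors are correlated, each sample variance is less precise than the test assumes, and the critical value is too small.

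This is the only inferential test specified for the first main endpoint. Under the written hypotheses, the excess error works against SMILE: it would be declared more variable than LASIK too often when the two are equal. The sample size carries the same assumption, so the power claim is exposed too.

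**Working it through.** **1. Reproduce the plan's figure.** Inputs from 9.2: R = (0.85/0.70)² = 1.4745 (stated as 1.47), one-sided alpha 0.05, power 0.80. For equal groups of n independent eyes,

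power = 1 - G(F₀.₉₅ / R),

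where G is the F distribution function with (n - 1, n - 1) degrees of freedom. The smallest n is 166 per group at R = 1.4745 and 169 at R = 1.47, and power at 168 v 168 is 80.5%. Other readings do not give 168: two-sided needs 211-214, a comparison with 480 LASIK eyes needs 98-100, and a one-sample chi-square test needs 81-82. Allowing for loss, 168/0.90 = 186.7, so 187. The arithmetic is sound for independent eyes. With 168 v 480 independent eyes, power is 92.1%.

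**2. Effect of pairing on a sample variance.** Let f be the share of eyes in pairs and rho the inter-eye correlation. For bivariate normal errors the squared errors of two fellow eyes have covariance 2·rho²·σ⁴, so

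Var(s²) ≈ (2σ⁴/n)(1 + f·rho²), with design effect D = 1 + f·rho².

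**3. Type I error of the unadjusted test.** On the log-variance scale the true standard error is √D times the assumed one when f and rho are the same in both cohorts. The error is then about 1 - Φ(1.645/√D). Example, f = 1 and rho = 0.5: D = 1.25, 1.645/1.118 = 1.471, error 7.1%.

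**4. Power of a test held at a true 5%.** Approximately Φ(ln R/(√D·SE) - 1.645), where SE = √(2/167 + 2/167) = 0.155 for 168 v 168, or √(2/167 + 2/479) = 0.127 for 168 v 480, and ln R = 0.388. Example, f = 1, rho = 0.5, 168 v 168: 0.388/(1.118 × 0.155) = 2.24, and Φ(2.24 - 1.645) is about 72%.

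**5. Results.** f and rho are assumed. Type I error is shown by formula and by simulation (40,000 normal trials per setting); power is from the simulation.

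| f | rho | D | Type I, formula | Type I, 168 v 168 | Type I, 168 v 480 | Power at true 5%, 168 v 168 | Power at true 5%, 168 v 480 |
|---|---|---|---|---|---|---|---|
| 1 | 0.3 | 1.09 | 5.8% | 5.7% | 5.7% | 77.2% | 90.0% |
| 1 | 0.5 | 1.25 | 7.1% | 7.2% | 6.9% | 72.0% | 86.7% |
| 1 | 0.7 | 1.49 | 8.9% | 8.8% | 8.5% | 65.6% | 80.9% |
| 0.5 | 0.3 | 1.045 | 5.4% | 5.4% | 5.4% | 78.8% | 91.0% |
| 0.5 | 0.5 | 1.125 | 6.1% | 6.2% | 6.0% | 76.1% | 89.5% |
| 0.5 | 0.7 | 1.245 | 7.0% | 6.7% | 7.1% | 72.9% | 86.3% |

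The type I error hardly depends on the comparator's size; the power does.

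**The case against.** **Power holds against the named comparator.** Section 9.2 names 480 LASIK eyes and no group of 168. Against 480, power never falls below 80% in the table. This stands. The loss below 80% applies to the calculation that yields 168, not to a comparison with all 480 eyes. The error rate is exceeded with either comparator.

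**The correlation may be low.** The endpoint is error about target, so the preoperative myopia shared by the two eyes is largely subtracted. At rho 0.1 to 0.2 with all eyes paired, D is 1.01 to 1.04 and the formula gives 5.1% to 5.3%, which is close to nominal. This also stands, but the documents give no value of rho, so a low one cannot be taken for granted.

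**Correcting the test makes excess scatter harder to detect.** Not rejecting is the favourable result for SMILE. With 168 v 480 and all eyes paired, the chance of detecting 0.85 v 0.70 D falls from 89.5% (unadjusted) to 84.5% at rho 0.5, and from 87.0% to 78.4% at rho 0.7, under the rule proposed below. This is a real cost and should be disclosed. It does not justify a test whose level is not the one stated.

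**The study may intend one eye per patient.** The singular wording leaves that open, but no rule says so.

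**Conclusion.** The concern holds. The plan's arithmetic is right for independent eyes, but nothing in the protocol makes them independent. If fellow eyes enter and their errors are correlated, the type I error exceeds 5%: by under one point at rho 0.3, and by up to about four points at rho 0.7 with every eye paired, which is the ceiling of the range examined. On the equal-group basis that reproduces 168, power at a true 5% is about 66-79%; against 480 LASIK eyes it is about 81-91%.

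These figures assume normal errors, the same f and rho in both cohorts, f of 0.5 or 1, and rho from 0.3 to 0.7. The F-test is also sensitive to tail shape, but the documents give no evidence on that and the conclusion does not rest on it. The point should be corrected; it does not invalidate the study.

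**What to change.** **Change to 9.1 and 9.2.** Keep the one-sided comparison and all eyes, and base the standard error on patients:

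- Estimate ln(SD SMILE / SD LASIK). Bootstrap it by resampling patients, keeping both eyes together, in both cohorts.
- Lower limit = estimate - 1.645 × bootstrap standard error. Reject equality if it exceeds 0.
- Report patients as well as eyes, and the bilateral share, in each cohort where known.
- Restate power against the comparator actually used, with D = 1 + f·rho² for rho 0.3 to 0.7.

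In simulation (168 v 480; 2,000 trials and 400 resamples per setting; Monte Carlo error about 0.5 point) this rule had type I error 4.1-5.9% over seven settings with rho 0 to 0.7. With all eyes paired its power was 89.9%, 84.5% and 78.4% at rho 0.3, 0.5 and 0.7.

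**If LASIK patient identifiers cannot be retrieved.** Bootstrap SMILE only, and take the LASIK standard error as √(D/(2 × 479)), shown for D from 1 to 1.5. With SMILE D = 1.25, the combined standard error moves only from √(1.25/334 + 1/958) = 0.069 to √(1.25/334 + 1.5/958) = 0.073. Simulated type I error was 3.3-6.1%. This fallback assumes normal LASIK errors, and its power was not simulated.

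**Simpler alternative.** Analyse one prespecified eye per patient. If all eyes are paired, this leaves 84 v 240 and 70% power, or 55% for 84 v 84. If one eye per patient is what was meant, a sentence saying so settles the SMILE side.

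**Cost.** Wording, a short script and a lower stated power. SMILE eyes can be grouped by the per-patient code in 12.3. The LASIK series comes from the study team's own earlier work, which suggests access to identifiers but does not confirm it. Because detection falls somewhat, failure to reject should not be presented as proof that the variances are equal. Judging SMILE by an upper limit against 0.15 D would be a separate change and is not proposed here.
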